2.5 Safety Analyses

All safety analyses will be performed on the SS.

2.5.1 Adverse Events

2.5.1.1 Derivation of Adverse Events

Adverse events (AEs) will be coded using MedDRA. They will be classified as follows:

Pre-treatment adverse event – An adverse event that starts between the date of signing the informed consent form (ICF) and the study treatment

Treatment-emergent adverse event (TEAE) – An adverse event that starts on or after the start of study treatment

Treatment-emergent adverse events of special interest (AESI) - The following are called out as AESIs in the protocol: catheter related infection, thrombophlebitis, dyspnea, cyanosis, allergic reactions, hyperlipemia, hypercoagulability, nausea, vomiting, headache, flushing, increase in temperature, sweating, sleepiness, pain in the chest and back, slight pressure over the eyes, dizziness, irritation at the site of infusion, hepatomegaly, splenomegaly, thrombocytopenia, leukopenia, and overloading syndrome (focal seizures, fever, leukocytosis, hepatomegaly, splenomegaly and shock). A blinded review of AEs will be conducted at the end of the study before unblinding to flag AESIs.

An adverse event will be considered related to study treatment if they respond 'Probably related' or 'Possibly related' to relationship to study treatment.

In case of incomplete information on study treatment or AE onset, events will be classified as treatment-emergent unless there is sufficient data to rule out the possibility that the event started after the start of study treatment.

If the severity of an adverse event is missing, then that adverse event will be classified as *severe*. If relationship of an adverse event is missing, then that adverse event will be classified as *probably related*.

The number of events per 100 patient days will be calculated as follows:

$$\frac{\text{Number of Total Events}}{\sum_{i=1}^{n} (\text{End Date of Treatment}_{i} - \text{Start Date of Treatment}_{i} + 1)}, \\100$$

where i represents each patient and n represents the total number of patients in the Safety Set for that treatment group.

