6.13.1 Performing Adverse Events Assessments

During the course of the study, and maximum 30 days after the last dose of study drug, if hospital discharge has not occurred, the Investigator or designee will routinely monitor and solicit each patient for the occurrence of any AEs. If an AE occurs, a full description of the event, including the date and time of onset, duration, severity, actions taken, outcome, seriousness of the event, and causal relationship of the AE to the study treatment will be recorded in the patient's CRF. All AEs will be followed by the Investigator until the event has resolved, stabilized, or returned to baseline.

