6.14 Removal of Patients from the Study/ Discontinuation of the Study

Any patient/legal representative may voluntarily withdraw consent for continued participation and data collection at any time during the course of the study. The Investigator may terminate a patient's study participation at any time during the study if the Investigator judges it to be in the patient's best interest.

Patients may be withdrawn or prematurely discontinued from the study treatment/assessments for any of the following reasons:

- Adverse Event(s)
- Clinically significant change in a laboratory parameter
- Protocol violation (i.e. patient failed to meet protocol entry criteria or did not adhere to the protocol requirements)
- Pregnancy
- Patient or any legal representative requests to withdraw from the study
- Sponsor or Investigator terminates the study

All patients randomized to Clinolipid who must receive Intralipid for rescue therapy purposes will be discontinued from the trial.

Parenteral nutrition therapy may be interrupted and restarted (based on the initial randomization) within a 1 to 2-day window, subject to adjudication from the medical monitor who conducts a clinical review of current patient status, assessment of any potential AE/SAEs, discussion/clarification with the investigator to resume or abort study treatment. The outcome of the adjudication process will not preclude the monitoring for AE/SAEs for the subsequent 30 days and in the event of an AE, following the subject until the AE resolves, stabilizes or the subject returns to baseline. If there is a likelihood that the patient will require restart of PN within 1 to 2 days of the initial stoppage, then it is recommended to delay performing the End of Study Treatment procedures. However, the End of Study Treatment procedures should be completed within 2 days of the initial stoppage if the patient has not restarted PN, as per Section 7.2.4 and Appendix 1 Schedule of Events.

If a patient's participation is discontinued, the reason(s) must be recorded in the source documents and in the CRF.

End of study treatment procedures should be performed when a patient withdraws or is discontinued from the study.

Patients who are withdrawn from the study will not be replaced.

The study may be discontinued:

- If new safety information becomes available indicating that continuing the study treatment or procedures may jeopardize the safety of the patients
- Because of an administrative decision by the Sponsor

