9.6.3 Safety Profile of Clinolipid and Intralipid

Vital signs and clinical laboratory tests will be summarized using descriptive summary statistics (number of patients, mean, standard deviation, median, minimum, and maximum) in each of the 2 treatment groups during the study period.

The following neonatal morbidities will be summarized by treatment group using n and percentage: BPD, ROP, IVH, PVL, NEC, and late-onset sepsis in enrolled premature infants born <37 weeks of gestation up to 1 month CA.

All AEs, SAEs, and AESIs will be tabulated by body system using the Medical Dictionary for Regulatory Activities (MedDRA) coded terms. They will be presented by treatment group using frequencies and percentage.

Adverse events of special interest are known AEs related to PN with ILEs, per Intralipid and Clinolipid USPIs and include the following: catheter related infection, thrombophlebitis, dyspnea, cyanosis, allergic reactions, hyperlipemia, hypercoagulability, nausea, vomiting, headache, flushing, increase in temperature, sweating, sleepiness, pain in the chest and back, slight pressure over the eyes, dizziness, irritation at the site of infusion, hepatomegaly, splenomegaly, thrombocytopenia, leukopenia, and overloading syndrome (focal seizures, fever, leukocytosis, hepatomegaly, splenomegaly and shock).

In addition, the AE rate will be estimated using person time (person-day) as the denominator, which is computed as "total number of patients" times "treatment exposure period [day]" in the corresponding treatment group. The AE rate per 100 patient days will be reported for the overall study period, and may be stratified into Weeks 1, 2, 3, and 4 as appropriate.

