- ^k Parenteral nutrition therapy may be interrupted and restarted (based on the initial randomization) within a 1 to 2-day window, subject to adjudication from the medical monitor who conducts clinical review of current patient status, assessment of any potential AE/SAEs, discussion/clarification with investigator to resume or abort study treatment. If there is a likelihood that the patient will require restart of PN within 1 to 2 days of the initial stoppage, then it is recommended to delay performing the End of Study Treatment procedures. However, the End of Study Treatment procedures should be completed within 2 days of the initial stoppage if the patient has not restarted PN.

Evaluation	Evaluation Screening Baseline	Baseline ^a	ie ^a Daily	Study Treatment Day (every 15 days ±2 days)					End of Study Treatment ^o
				15	30	45	60	75	or Day 90 (± 2 days)

¹ When breastfeeding intakes cannot be measured, the best estimation (volume) of the investigator will be recorded.

^mMedications and nutrition supplements received within 30 days prior to randomization by the patient and the nursing mother (if applicable) also will be recorded at Screening. The nursing mother's medication history will be collected from the patient's chart (if available).

ⁿ Adverse events occurring prior to the initiation of the first study procedure will be recorded as signs and symptoms in the patient's medical history. During the course of the study, and for 30 days after the last dose of study drug, the Investigator or designee will routinely monitor and solicit each patient for the occurrence of any AEs. All SAEs or any pregnancy reports with or without an associated SAE must be reported to Baxter Global Pharmacovigilance within 24 hours of site's knowledge of the event.

^o End of study treatment is defined as the last day of PN with Intralipid or Clinolipid; maximum 90 days of study treatment is allowed. After 90 days, the patient will receive nutritional intervention as prescribed by their healthcare provider if still required.

Fatty Acid	Chain Length	Reference Values
Lauric Acid	C12:0	<1 year: 6-190 nmol/mL
		1-17 years: 5-80 nmol/mL
		> or =18 years: 6-90nmol/mL
Myristic Acid	C14:0	<1 year: 30-320 nmol/mL
		1-17 years: 40-290 nmol/mL
		> or =18 years: 30-450 nmol/mL
Hexadecenoic Acid	C16:1n-9	<1 year: 21-69 nmol/mL
		1-17 years: 24-82 nmol/mL
		> or =18 years: 25-105 nmol/mL
Palmitoleic Acid	C16:1n-7	<1 year: 20-1,020 nmol/mL
		1-17 years: 100-670 nmol/mL

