ⁿ Adverse events occurring prior to the initiation of the first study procedure will be recorded as signs and symptoms in the patient's medical history. During the course of the study, and for 30 days after the last dose of study drug, the Investigator or designee will routinely monitor and solicit each patient for the occurrence of any AEs. All SAEs or any pregnancy reports with or without an associated SAE must be reported to Baxter Global Pharmacovigilance within 24 hours of site's knowledge of the event.

° End of study treatment is defined as the last day of PN with Intralipid or Clinolipid; maximum 90 days of study treatment is allowed. After 90 days, the patient will receive nutritional intervention as prescribed by their healthcare provider if still required.

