2.5.1.2 Analysis of Adverse Events

An AE overview summary table will be prepared to include the number of patients, the percentage of patients (%), and the number of events per 100 patient days by treatment group, for the following categories:

- 1. Any AE
- 2. Any treatment-emergent adverse event (TEAEs)

- 3. Treatment emergent non-serious AEs
- 4. Treatment-emergent serious AEs (SAEs)
- 5. Treatment-emergent AEs of special interest (AESIs)
- 6. Treatment-emergent AEs related to study treatment
- 7. Treatment-emergent SAEs related to study treatment
- 8. Treatment-emergent AEs leading to death

Additional listings and tables on the above categories (with the exception of #1) will be given by SOC and PT. Pre-treatment adverse events (those occurring between informed consent and treatment) will also be listed. For SAE listings, the seriousness criteria will be included in the listing.

The tables below will display the total number of patients, the percentage of patients (%), the number of events, the number of events per 100 patient days, system organ class (SOC), and preferred term by treatment group. Table summaries will be produced for:

- Treatment-emergent AEs by severity
- Treatment-emergent SAEs by severity
- Treatment-emergent AEs by relationship to study treatment
- Treatment-emergent SAEs by relationship to study treatment
- Treatment-emergent adverse events in ≥5% of patients (in either Clinolipid or Intralipid group)

Tables by preferred term and tables by system organ class (SOC) and preferred term will be sorted in descending order by the percentage of patients.

Adverse event listings will be sorted by patient ID and adverse event start date. They will include primary AE number, SOC, PT, verbatim term, adverse event start and end date and its duration, treatment date, relationship to study treatment, alternate causality, severity, action taken, seriousness, outcome, whether the event is ongoing, and whether AE led to discontinuation from study.

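### Adverse event rates count events with no stated closing date over treatment days only, and the AESI list used for flagging leaves out three named events

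*SAP*

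**What the plan says.** **Rate.** SAP 2.5.1.1 defines a TEAE as "An adverse event that starts on or after the start of study treatment" and gives no last date. Under "The number of events per 100 patient days will be calculated as follows", total events are divided by the summed treatment days (end date minus start date of treatment, plus 1) of the Safety Set patients in the arm, scaled to 100. SAP 2.5.1.2 then reports "the number of events per 100 patient days by treatment group, for the following categories". Eight categories follow, including any AE, TEAEs, treatment-emergent SAEs and AESIs, and the rate recurs in the tables by system organ class and preferred term. In Protocol 9.6.3 "the AE rate will be estimated using person time (person-day) as the denominator", built from the number of patients and the treatment exposure period.

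**Collection.** Protocol 6.13.1 solicits AEs for "maximum 30 days after the last dose of study drug, if hospital discharge has not occurred". Footnote n of Protocol Appendix 1 reads "During the course of the study, and for 30 days after the last dose of study drug, the Investigator or designee will routinely monitor", and footnote n of the SAP 1.4.5 schedule says "for 30 days after the last dose of study drug, the Investigator or designee will routinely monitor and solicit each patient". Neither footnote mentions discharge. Protocol 6.14, on interruptions of PN, says that the adjudication outcome "will not preclude the monitoring for AE/SAEs for the subsequent 30 days". Protocol 6.13.7.2 has SAEs reported until 30 days after the last dose. Protocol 6.13.8 closes TEAEs at the end of the study.

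**AESIs.** Protocol 2.2, SAP 1.3 and SAP 1.6.2 share one list. Protocol 9.6.3 and SAP 2.5.1.1 share a shorter one. SAP 2.5.1.1 describes the blinded flagging of AESIs directly after the shorter list.

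**The concern.** A rate describes a defined period only if its events and its time come from the same days. Here the SAP lets in events for as long as they are collected but stops the clock at the last dose. An event starting after that raises the rate without adding time, so the result is neither an on-treatment rate nor a rate over the whole observation period.

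No hypothesis test is planned (SAP 1.4.2), so the printed rates are themselves results that readers will compare between arms. If treatment time, follow-up time or the off- to on-treatment AE rate ratio differs by arm, the comparison shifts as well. Protocol 6.14 gives one reason why treatment time could differ: patients randomized to Clinolipid who need Intralipid as rescue are discontinued, a rule with no counterpart in the other arm.

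The AESI point is simpler. SAP 2.5.1.1 presents its list as the one named in the protocol, but it is shorter than the definition in the protocol's objectives. An AESI table and rate built from it would contradict that definition.

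**Working it through.** **1. Plan's own figure.** There is none to reproduce. The documents give no AE rate, mean exposure, post-treatment stay or share of late onsets.

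**2. Size of the mismatch.** Let N be the TEAEs counted, D the summed treatment days and p the share of the N with onset after the on-treatment window.

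- Rate as the SAP is written: 100 × N / D.
- On-treatment rate over the same D: 100 × (1 − p)N / D.
- Ratio: 1/(1 − p).

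p = 0, 10, 20, 25 and 50% gives 1.00, 1.11, 1.25, 1.33 and 2.00.

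**3. What could produce such a p.** Let T be mean treatment days, F mean post-treatment days under AE collection and r the off- to on-treatment AE rate ratio. With the window closing at the last dose, p = rF/(T + rF) and the ratio is 1 + rF/T. All values below are assumptions.

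| T | F | r | p | Ratio |
|---|---|---|---|---|
| any | 0 | any | 0% | 1.00 |
| 30 | 10 | 0.5 | 5/35 = 14.3% | 1.17 |
| 30 | 10 | 1 | 10/40 = 25% | 1.33 |
| 30 | 30 | 0.5 | 15/45 = 33.3% | 1.50 |
| 30 | 30 | 1 | 30/60 = 50% | 2.00 |

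With F = 10 and r from 0.5 to 1, the ratio is 1.36 to 1.71 at T = 14 and 1.08 to 1.17 at T = 60.

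**4. Arm comparison.** With T, F and r equal in both arms, the factor cancels. Otherwise, again with assumed values:

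- Treatment time differs, true rates equal, T = 20 vs 25. F = 10: 1.25/1.20 = 1.04 (r = 0.5) and 1.50/1.40 = 1.07 (r = 1). F = 30: 1.75/1.60 = 1.09 and 2.50/2.20 = 1.14.
- A true ratio of 2.0 that ends with treatment, T = 30, control r = 1: (60 + 10)/(30 + 10) = 1.75 for F = 10, and (60 + 30)/(30 + 30) = 1.50 for F = 30.
- A delayed effect with equal on-treatment rates, T = 30, F = 10, r = 1 vs 0.5: (1 + 10/30)/(1 + 5/30) = 40/35 = 1.14.

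**5. Any AE row.** As worded, it also puts pre-treatment events over treatment days. These are probably few, because Protocol 7.1 sends non-serious screening events to the medical history.

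**6. AESI lists, item by item.** The list in Protocol 2.2, SAP 1.3 and SAP 1.6.2 has 26 items; the list in Protocol 9.6.3 and SAP 2.5.1.1 has 23. The three missing items are EFAD, jaundice and transient increases in liver function tests. None is added.

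**The case against.** The strongest reply is that the protocol already closes the TEAE period. Protocol 6.13.8 ends it with the study, Protocol 3.1 and SAP 1.4.1 describe only a screening and a treatment period, and the schedule has no visit after the End of Treatment visit. The collection clauses name the course of the study first and the 30 days as an addition, which suggests that those days lie outside it. The SAP rests on this protocol and its section 3 declares no changes. On that reading, late onsets are not TEAEs and the TEAE rates are not inflated.

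This reading is fair, and it makes the overstatement conditional. It does not settle the matter. The end of the study is not defined, SAP 2.1.3 ties a patient's completion to finishing the study procedures without saying whether the 30-day monitoring is one of them, and a programmer following SAP 2.5.1.1 would find no closing date to apply.

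Other parts of the reply also stand. Events per 100 treatment days is the protocol's own choice, and counting delayed reactions against exposure can be defended, provided that it is stated. Under Protocol 6.13.1 AE solicitation stops at discharge, so 30 fully observed days may be uncommon. The Protocol 6.14 remark on 30 days arises from PN interruptions and is weak support for a general window. On AESIs, SAP 2.5.1.1 does not say outright that the blinded review is confined to its list, and Protocol 9.6.3 introduces its list as inclusive. The two lists still disagree within each document.

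**Conclusion.** Two points are certain from the text. The SAP gives TEAEs no closing date and divides by treatment days, while collection runs past the last dose. The shorter AESI list omits three events that the fuller one names.

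The size of the rate effect is not known. It is a factor of 1/(1 − p) on the AE, SAE and AESI rates per 100 patient-days, and p may be zero. The figures above, 2.00 included, rest on assumed durations and rate ratios. Counts and percentages do not change, and the EFAD and PNALD rates have their own person-time (SAP 2.4.1.1 and 2.4.2.2.1).

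A reader might infer three stronger things:

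- *The rates will be materially overstated, perhaps doubled.* The documents give neither late onsets nor follow-up time, and one reading of Protocol 6.13.8 removes the effect from the TEAE rates.
- *The arm comparison is biased against Clinolipid.* The one-arm rescue rule could shorten treatment there, but no figure shows that it does, and the factor cancels when T, F and r are equal.
- *EFAD and liver events would go unreported.* EFAD is the primary endpoint, liver tests and bilirubin have their own tables, and jaundice recorded as an AE still appears in the AE tables. What is lost is their place in the AESI table and rate.

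This should be corrected before unblinding. It does not touch the primary endpoint.

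**What to change.** **(a) Rates, SAP 2.5.1.1 and 2.5.1.2.** Keep the form of the formula, the Safety Set definition of n and the existing TEAE partial-date rule. For every rate per 100 patient-days, including the any-AE row, count only TEAEs with onset from the start of treatment to the end of a stated on-treatment window, and sum the denominator over the same window. The window should cover the End of Treatment visit, which may fall 2 days after the last dose (Protocol 7.2.4 and Appendix 1), so that findings first made there are not lost. A TEAE with a partial onset date counts unless the date shows onset after the window. Show the on-treatment event count beside each rate, and keep later onsets in the overall TEAE counts and percentages.

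**(b) Definitions.** Define the end of the study in Protocol 6.13.8, carry the TEAE closing date into the SAP and align Protocol 9.6.3. Reconcile the discharge condition in Protocol 6.13.1 with footnote n in both documents.

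**(c) AESIs.** Use the full Protocol 2.2 list in SAP 2.5.1.1 and Protocol 9.6.3 before the blinded flagging.

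**Cost.** Some wording and programming, from onset and treatment dates already collected. Two event counts will need clear labels, and the any-AE rate will equal the TEAE rate. Reported rates may be lower, partly because the window adds up to 2 days per patient: at an assumed mean of 30 treatment days, the denominator grows by 32/30 = 1.07 even if p is zero. Delayed reactions that start after the window leave the rate and stay visible only in counts and percentages.

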2.5.1.2 Analysis of Adverse Events

An AE overview summary table will be prepared to include the number of patients, the percentage of patients (%), and the number of events per 100 patient days by treatment group, for the following categories:

- 1. Any AE
- 2. Any treatment-emergent adverse event (TEAEs)

- 3. Treatment emergent non-serious AEs
- 4. Treatment-emergent serious AEs (SAEs)
- 5. Treatment-emergent AEs of special interest (AESIs)
- 6. Treatment-emergent AEs related to study treatment
- 7. Treatment-emergent SAEs related to study treatment
- 8. Treatment-emergent AEs leading to death

Additional listings and tables on the above categories (with the exception of #1) will be given by SOC and PT. Pre-treatment adverse events (those occurring between informed consent and treatment) will also be listed. For SAE listings, the seriousness criteria will be included in the listing.

The tables below will display the total number of patients, the percentage of patients (%), the number of events, the number of events per 100 patient days, system organ class (SOC), and preferred term by treatment group. Table summaries will be produced for:

- Treatment-emergent AEs by severity
- Treatment-emergent SAEs by severity
- Treatment-emergent AEs by relationship to study treatment
- Treatment-emergent SAEs by relationship to study treatment
- Treatment-emergent adverse events in ≥5% of patients (in either Clinolipid or Intralipid group)

Tables by preferred term and tables by system organ class (SOC) and preferred term will be sorted in descending order by the percentage of patients.

Adverse event listings will be sorted by patient ID and adverse event start date. They will include primary AE number, SOC, PT, verbatim term, adverse event start and end date and its duration, treatment date, relationship to study treatment, alternate causality, severity, action taken, seriousness, outcome, whether the event is ongoing, and whether AE led to discontinuation from study.

